4.2.2.1.1 Close monitoring for AEs based on concomitant therapy

If a patient is taking concomitant therapy that is metabolised by CYP3A4 and / or CYP2C8, which has a narrow therapeutic index and / or is a sensitive substrate, close monitoring for AEs is recommended in this trial (also refer to Table [1.4.2: 1](#)). A list to support the

identification of the above-mentioned concomitant therapies will also be provided in the ISF. The list will not claim completeness.

4.2.2.2 Restrictions on diet and lifestyle

Drastic changes of diet and lifestyle in the course of the trial should be avoided. This includes unusual and strenuous exercise for the patient (e.g. taking up exercises that put pressure on the abdomen, such as weightlifting).

Alcohol consumption must be avoided throughout the trial; excessive alcohol consumption could lead to hypotension when taken concomitantly with BI 685509. During the treatment period, patients will be asked if they have consumed any alcohol, and where necessary, reminders should be issued to abstain from alcohol consumption.

The requirement for a fasting status upon arrival at clinic visits is as defined in the [Flow Chart](#). Once all visit assessments are complete that require this status, the patient may eat as normal.

4.2.2.3 Contraception requirements

WOCBP (for the definition refer to Section [3.3.2](#)) must be ready and able to use a highly effective method of birth control from the randomisation visit (Visit 2) until 7 days after the last trial medication intake, if their partner is a male able to father a child. No contraceptive is required for the partner of the WOCBP.

Highly effective methods of birth control per ICH M3 (R2) that result in a low failure rate of less than 1% per year when used consistently and correctly include (if local regulations permit):

- combined (oestrogen and progestogen containing) hormonal birth control that prevents ovulation (oral, intravaginal, transdermal)
- progestogen-only hormonal birth control that prevents ovulation (oral, injectable, implantable)
- intrauterine device (IUD) or intrauterine hormone-releasing system (IUS)
- bilateral tubal occlusion

A male patient must use a condom with or without spermicide until at least 7 days after last trial medication intake if their sexual partner is a WOCBP, or, be vasectomised with documented absence of sperm in the ejaculate. No contraceptive is required for the male patient's partner.

Alternatively WOCBP and male patients able to father a child must abstain from male-female sex. This is defined as being in line with the preferred and usual lifestyle of the patient. Periodic abstinence e.g. calendar, ovulation, symptothermal, post-ovulation methods; declaration of abstinence for the duration of exposure to trial medication; and withdrawal are not acceptable.

4.3 TREATMENT COMPLIANCE

Patients are requested to bring all remaining trial medication including empty package material with them when attending visits.

Based on tablet counts, treatment compliance will be calculated as shown in the formula below. Compliance will be verified by the CRA authorised by the Sponsor or delegate.

$$\text{Treatment compliance (\%)} = \frac{\text{Number of tablets actually taken}}{\text{Number of tablets which should have been taken as directed by the Investigator}} \times 100$$

If the number of doses taken is not between 80-120%, site staff will explain to the patient the importance of treatment compliance.

5. ASSESSMENTS

5.1 ASSESSMENT OF EFFICACY

5.1.1 Hepatic venous pressure gradient

HVPG measurement will be performed at the time points specified in the [Flow Chart](#). Sites must have access to the necessary infrastructure and equipment to measure HVPG (e.g. a hepatic haemodynamic laboratory at their site, or at a nearby institution). Site staff performing the procedure must have sufficient expertise (e.g. performing in the region of 25 or more HVPG measurements per year) with interventional skills and expertise in the reading of pressure tracings, since a local interpretation of the tracing from Visit 1c will be required for eligibility purposes (refer to Section [3.3.2](#)).

[figure not shown]
The HVPG procedure within the trial will be conducted in a standardised fashion at all sites (for details refer to the HVPG manual in the ISF); training will be provided. Each trial site will be asked to provide acceptable sample HVPG tracing(s) prior to commencing patient recruitment. Measurements of wedged hepatic venous pressure (WHVP) and free hepatic venous pressure (FHVP) will be performed in triplicate; tracings will be provided to an external Supplier and read centrally by independent expert(s) in PH; the central read will include a subjective assessment of the overall trace quality as well as a read of the relevant pressures. The independent expert(s) will be blinded to the timepoint that the trace relates to. The central read will include the traces from Visit 1c that have also been interpreted locally. The results of the central read will be transferred to the Sponsor and will be considered the official evaluation of the trial. In case of discrepancies between a local interpretation and the central evaluation (e.g. of the Visit 1c tracing), the central evaluation will remain valid.

HVPG measurements should be performed using the same hepatic vein, prior to intake of the trial medication, after an overnight fast, and ideally in the morning. If it is not possible to perform the measurement at Visit 1c in the morning an alternative time of day can be chosen; in this case, a fast of at least four hours is required. All subsequent HVPG measurements must then be performed at approximately the same time of day as the Visit 1c measurement for a single patient.

If Visit 1b and 1c are performed on the same day, the HVPG measurement must be performed after the gastroscopy (i.e. only once it is confirmed that the patient remains eligible for the trial). During the treatment period, following randomisation, HVPG measurements should be performed on the day of the scheduled visit, or within seven days (if this latter approach is taken, the measurement should still be performed after an overnight fast / after a fast of at least four hours). If an alternative time of day (i.e. not in the morning, see above) has been chosen for treatment period HVPGs, the morning dose of trial medication can be taken prior to the procedure. In the event of early discontinuation from the trial, refer to Section [6.2.2.1](#) for guidance regarding the HVPG measurement at the ED visit.

A summary of the HVPG procedure is as follows ([R20-3977](#)):

Under local anaesthesia and ultrasound guidance, a catheter introducer sheath is placed in the right internal jugular vein. Using fluoroscopic guidance, a balloon catheter is advanced into the inferior vena cava (IVC) and inserted into a large hepatic vein. Correct and sufficient wedge position of the catheter is ensured by injecting contrast media while the balloon is blocking the outflow of the cannulated hepatic vein. After calibrating the external pressure transducer, continuous pressure recordings are obtained with triplicate recordings of the WHVP and FHVP. The difference between FHVP and WHVP is referred to as HVPG, with values ≥ 10 mmHg indicating CSPH. Before removing the catheter, pressure readings obtained in the IVC at the same level, as well as the right atrial pressure, are recorded.

5.2 ASSESSMENT OF SAFETY

5.2.1 Physical examination

A complete physical examination must be performed at the three time points specified in the [Flow Chart](#); further physical examinations are only required if the patient reports symptoms. A complete physical examination includes, as a minimum, general appearance, neck, lungs, cardiovascular system, abdomen, extremities and skin.

5.2.1.1 Anthropometric measurements (height, weight, waist and hip circumference)

Measurement of height, body weight, waist and hip circumference will be performed at the time points specified in the [Flow Chart](#). Height will be measured at Visit 1a only. The results of anthropometric measurements must be included in the source documents available at the site.

Whenever possible, weight measurements should always be performed on the same weighing scales for one patient. In order to get comparable body weight values, the assessment should be performed in the following way:

- shoes, coat / jackets and any headgear⁵ should be taken off
- pockets should be emptied of heavy objects (i.e. keys, coins etc)
- after bladder voiding

The measuring tape used for waist and hip circumference should be made of a material that is not easily stretched, such as fiberglass. Waist circumference measurements should be made around a patient's bare midriff, after the patient exhales while standing without shoes and with both feet touching and arms hanging freely. Waist circumference should be determined by measuring the midpoint between the lowest rib and the iliac crest. The tape should be placed perpendicular to the long axis of the body and horizontal to the floor and applied with sufficient tension to conform to the measurement surface.

Hip circumference measurements should start at one hip, wrapping the measuring tape around the widest part of the buttocks, and around the other hip to the front. Coats / jackets should be taken off and pockets emptied to ensure a close measurement and with both feet touching and arms hanging freely.

⁵Headgear worn for religious reasons is acceptable, but this should be worn for all weight measurements in the trial

5.2.2 Vital signs / home blood pressure and heart rate monitoring

Vital signs (SBP, DBP, as well as HR [pulse rate]) will be evaluated at trial visits at the time points specified in the [Flow Chart](#), prior to blood sampling and prior to the 12-lead ECG. BP measurements should be recorded in the eCRF to the nearest 1 mmHg. BP measurements should be performed on the non-dominant arm. HR should be measured electronically or by palpation, and counted for one minute. BP and HR measurements should be taken after patients have rested quietly, in the seated / supine position, for at least 5 minutes. The measurements recorded at the trial visit must be included in the source documents available at the site.

At screening (Visit 1a), the site should use their preferred method to measure vital signs. From Visit 2 onwards, vital signs should be measured using the patients home BP monitoring equipment (refer to Section [5.2.2.1](#)) in order to have a consistent method for the duration of the trial. This includes the pre- and post-dose vital signs measurements during the dose-titration period and at the subsequent visit (refer to the [Flow Chart](#) and Section [6.2](#)).

5.2.2.1 Home blood pressure and heart rate monitoring

Home BP and HR monitoring will be performed by the patient as specified in the [Flow Chart](#). Electronic BP and HR monitoring equipment will be provided for this purpose. Site staff will train the patient in the correct use of the equipment at Visit 2, explaining that it must be used only to record BP and HR measurements belonging to the patient. Subsequent refresher training should be provided at subsequent visits if required.

Patients will be asked to measure their BP and HR every day in the mornings, soon after waking up prior to much physical activity, and after resting seated for approximately 5 minutes. Measurements must be taken before administration of the morning dose of trial medication. The electronic readings will be stored in the memory of the home BP and HR monitoring equipment.

If, at any time after trial medication intake, a patient experiences symptoms suggestive of hypotension (e.g. he / she feels light-headed / dizzy, sees black spots, suffers from weakness etc.), particularly if the symptoms occur whilst standing up, or if he / she has any other symptoms in between trial visits, additional BP and HR reading(s) can be taken and the patient should report these symptoms at the next trial visit. The patient should bring the home BP and HR monitoring equipment with them to each trial visit (refer to the [Flow Chart](#)) for the site staff to review the electronic readings, and to use for the measurement of BP and HR during trial visits from Visit 2 onwards (refer to Section [5.2.2](#)). Any BP / HR measurements which, following review, are evaluated as AEs, must be included in the source documents available at the site (refer to Section [8.3.1](#)).

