2.1.3 Secondary endpoints

Secondary endpoints include:

- percentage change in HVPG from baseline (measured in mmHg) after 8 weeks of treatment
- response defined as > 10% reduction from baseline HVPG (measured in mmHg) after 8 weeks of treatment
- response defined as > 10% reduction from baseline HVPG (measured in mmHg) after 24 weeks of treatment
- occurrence of one or more decompensation events (i.e. ascites, VH, and / or overt HE) during the 24 week treatment period
- occurrence of CTCAE grade 3 (or higher) hypotension or syncope based on Investigator judgement, during the first 8 weeks of the treatment period
- occurrence of CTCAE grade 3 (or higher) hypotension or syncope based on Investigator judgement, during the 24 week treatment period
- occurrence of discontinuation due to hypotension or syncope during the first 8 weeks of the treatment period
- occurrence of discontinuation due to hypotension or syncope during the 24 week treatment period

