Following randomisation, the trial design includes a dose-titration period. The mechanism related vasodilatation of BI 685509 can lead to orthostatic dysregulation and hypotensive episodes (refer to Table [1.4.2: 1](#)). The orthostatic dysregulation is dose-limiting and clinical tolerability is improved if the dose is titrated. A *BID* administration also allows the total daily exposure of BI 685509 to be further increased while high peak concentrations are avoided. Hence, in this trial, a dose-titration regimen of [REDACTED] *BID* to [REDACTED] *BID* to [REDACTED] *BID* will be followed.

Patients selected for this trial have a risk for further progression into decompensation, a severe outcome. A DMC, independent from the Sponsor, will therefore be established to review unblinded safety data at intervals to identify any potential risks and / or the need for implementation of further safety measures. The tasks and responsibilities of the DMC members will be detailed in the DMC charter (refer to Section [8.7](#)).

An independent AC will also be established for blinded adjudication of hepatic injury. The tasks and responsibilities of the AC members will be detailed in the AC charter (refer to Section [8.7](#)).

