4.1.4.1 Rules for down-titration in case of intolerance to trial medication

If a patient has an AE that, based on Investigator judgement, may be related to trial medication, the down-titration rules below must be followed. These rules apply if the patient has successfully completed the dose titration period (i.e. Visit 4) and is either still taking their assigned dose of trial medication, or if they have missed ≤ 3 consecutive doses³. If the patient has not successfully completed the dose titration period (i.e. Visit 4), down-titration is not permitted; in case of persistent AEs or severe effects, the patient must permanently discontinue treatment (refer to Section 3.3.4.1).

- if the patient is currently receiving either [REDACTED] BID BI 685509 or [REDACTED] BID 685509 (or corresponding matching placebo) the dose will be down-titrated one level i.e.
 - [REDACTED] BID BI 685509 / matching placebo down-titrates to [REDACTED] BID BI 685509 / matching placebo
 - [REDACTED] BID BI 685509 / matching placebo down-titrates to [REDACTED] BID BI 685509 / matching placebo

Once down-titration has taken place, no further up-titration will be permitted.

³One dose refers to an individual time point e.g. morning dose or evening dose.

If a patient continues to have an AE, or a new AE develops, that based on Investigator judgement, may be related to trial medication, a second down-titration will be permitted. Depending on the randomisation assignment, this may be a pseudo down-titration i.e.:

- if the patient is currently receiving [REDACTED] BID BI 685509 or matching placebo the dose will be down-titrated to [REDACTED] BID BI 685509 matching placebo (a patient previously down-titrated to [REDACTED] BID BI 685509 matching placebo will be pseudo down-titrated)
- if the patient is currently receiving [REDACTED] BID BI 685509 or matching placebo the dose will be down-titrated to [REDACTED] BID BI 685509 / matching placebo

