4.1.4.2 Rules for re-starting up-titration in case of interruption of trial medication

An interruption of trial medication may have an influence on the tolerability. Hence, if a patient has missed > 3 consecutive doses⁴ of trial medication for any reason (e.g. due to an AE, or for compliance reasons), the rules below will apply for the safety of the patient. If ≤ 3 consecutive doses of trial medication have been missed and there is no related AE, then the next dose of trial medication should be taken as scheduled.

- after an interruption of trial medication of > 3 consecutive doses, the patient should re-start the dose titration period at [REDACTED] BID BI 685509 / matching placebo independent of the dose the patient was receiving previously
- before any further up-titration occurs the patient must have taken the preceding dose for at least 7 consecutive days. This applies throughout the treatment period
 - this may mean that a patient due to be up-titrated at Visit 3 or 4 (as per Table 4.1.4: 1) is held at their current dose until their next scheduled visit. They could also be up-titrated at an unscheduled visit once this requirement is met
- if interruption occurs after Visit 4, subsequent up-titration will be allowed either at a scheduled visit or at an unscheduled visit

Patients with an interruption of trial medication will need to return to the investigational site to receive their continuing supply of trial medication, either at the next scheduled visit or via an unscheduled visit.

[figure not shown]
⁴One dose refers to an individual time point e.g. morning dose or evening dose.

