7.8.1.5 User-defined adverse event category (UDAEC)

UDAEC will be summarized by dose group, primary system organ class and preferred term. In summary, Table [7.8.1.5:1](#) provides the definition of UDAECs according to AE category or Standardized MedDRA Query (SMQ).

Table 7.8.1.5: 1 Definition of continuous UDAEC

Category	Safety topic	Definition
UDAEC	Hypotension	Investigator-reported, as a dedicated AE category on the AE eCRF page
UDAEC	Syncope	Investigator-reported, as a dedicated AE category on the AE eCRF page
UDAEC	Acute kidney injury	SMQ 'Acute renal failure', narrow scope
UDAEC	Peripheral edema	SMQ 'Haemodynamic oedema, effusions and fluid overload'
UDAEC	Bleeding	SMQ 'Haemorrhages', narrow scope
UDAE	Liver events	Narrow sub-SMQ 'Liver related investigations, signs and symptoms', narrow sub-SMQ 'Cholestasis and jaundice of hepatic origin', narrow sub-SMQ 'Hepatitis, non-infectious' and narrow sub-SMQ 'Hepatic failure, fibrosis and cirrhosis and other liver damage-related conditions'

Summary of hypotension and syncope will be presented for both patient-based and event-based analyses.

Analysis on hypotension based on baseline BP and the lowest BP during the episode will be carried out. Criteria for significant (vs. non-significant) hypotensive episode are:

- Baseline SBP \leq 140: decrease $\left(\frac{\text{lowest SBP during the episode} - \text{baseline SBP}}{\text{baseline SBP}} \right) \geq 30\%;$
- Baseline SBP $>$ 140: decrease $\left(\frac{\text{lowest SBP during the episode} - \text{baseline SBP}}{\text{baseline SBP}} \right) \geq 40\%;$
- Or lowest SBP during the episode $<$ 90.
- Baseline DBP \leq 70: $\left(\frac{\text{lowest DBP during the episode} - \text{baseline DBP}}{\text{baseline DBP}} \right) \geq 30\%;$
- Baseline DBP $>$ 70: $\left(\frac{\text{lowest DBP during the episode} - \text{baseline DBP}}{\text{baseline DBP}} \right) \geq 40\%;$
- Or lowest DBP during the episode $<$ 50.
- Lowest mean arterial pressure (MAP = DP + 1/3(SP – DP)) during the episode $<$ 70.

The severity of hypotension will be categorised based on the CTCAE grades collected from the eCRF:

- CTCAE grade 1 – mild
- CTCAE grade 2 – moderate
- CTCAE grade 3, 4 or 5 – severe

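### Patients with symptoms suggestive of hypotension are told to report them at the next trial visit; a same-day call would remove a possible wait of 7 to 28 days (9 to 38 with visit windows)

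*Protocol*

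**What the plan says.** Protocol 5.2.2.1 covers symptoms such as dizziness or light-headedness after trial medication, and any other symptoms between visits. Its instruction is that "additional BP and HR reading(s) can be taken and the patient should report these symptoms at the next trial visit". The routine home reading is taken once a day, seated, soon after waking; "Measurements must be taken before administration of the morning dose of trial medication". Readings are held in the device memory, and the patient brings the device to each visit "for the site staff to review the electronic readings".

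Protocol 3.2 explains why titration is used: "The orthostatic dysregulation is dose-limiting and clinical tolerability is improved if the dose is titrated".

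The responses available to an intolerant patient are spread over four sections:

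- **4.1.4:** interruption of trial medication.
- **4.1.4.1:** down-titration, with the limit that "If the patient has not successfully completed the dose titration period (i.e. Visit 4), down-titration is not permitted". Before that point, persistent AEs or severe effects mean permanent discontinuation.
- **4.1.4.2:** a restart of titration at the lowest dose after more than 3 consecutive missed doses.
- **6.1:** unscheduled visits for safety, at the investigator's discretion.

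One secondary endpoint in Protocol 2.1.3 is "occurrence of CTCAE grade 3 (or higher) hypotension or syncope based on Investigator judgement, during the 24 week treatment period". SAP 7.8.1.5 adds: "Analysis on hypotension based on baseline BP and the lowest BP during the episode will be carried out".

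**The concern.** The written instruction sends the patient to the next scheduled visit, whenever that falls. The investigator cannot decide to interrupt, down-titrate, discontinue or recall a patient without knowing of the event, and the legible text gives the patient no prompt to say so earlier. What is at stake is continued dosing of a symptomatic patient for an effect that the protocol itself treats as dose-limiting.

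A smaller point concerns the data. The SAP classifies hypotensive episodes by the lowest blood pressure during the episode, while the reading that would supply it at home is left to the patient's choice.

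**Working it through.** **Inputs.** Planned days and windows come from the Protocol Flow Chart. Protocol 6.1 anchors every window to Day 1, not to the previous visit.

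**Check against the plan's own figures.** Planned day minus and plus the allowed days reproduces all eight legible per-protocol windows in SAP Table 6.7:2: V3 8–10, V6 40–46, V7 54–60, V8 80–90, V9 108–118, V10 136–146, EoT 164–174 and EoS 192–202. The V4 and V5 rows are masked there; the Flow Chart gives 15–17 and 29–31.

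**Formulas**, for a symptom that starts just after a visit:

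- Nominal wait = planned day of the next visit − planned day of the current visit.
- Maximum wait = latest allowed day of the next visit − earliest allowed day of the current visit.

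| Interval | Nominal wait (days) | Maximum wait (days) |
|---|---|---|
| V2–V3 | 8 − 1 = 7 | 10 − 1 = 9 |
| V3–V4 | 15 − 8 = 7 | 17 − 8 = 9 |
| V4–V5 | 29 − 15 = 14 | 31 − 15 = 16 |
| V5–V6 | 43 − 29 = 14 | 46 − 29 = 17 |
| V6–V7 | 57 − 43 = 14 | 60 − 40 = 20 |
| V7–V8 | 85 − 57 = 28 | 90 − 54 = 36 |
| V8–V9 | 113 − 85 = 28 | 118 − 80 = 38 |
| V9–V10 | 141 − 113 = 28 | 146 − 108 = 38 |
| V10–EoT | 169 − 141 = 28 | 174 − 136 = 38 |

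The 9 days for V3–V4 respect the titration rule in 6.1. A delayed Visit 3 forces a delayed Visit 4, but Visit 3 on Day 8 followed by Visit 4 on Day 17 is still allowed. EoT–EoS is off drug and is left out.

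At two doses a day, the nominal waits correspond to up to 7 × 2 = 14, 14 × 2 = 28 or 28 × 2 = 56 further doses.

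**Distance from the last planned dose step.** The last planned increase is at Visit 4 and the first 28-day interval starts at Visit 7. The nominal distance is 57 − 15 = 42 days, with a minimum of 54 − 17 = 37 and a maximum of 60 − 15 = 45. The longest waits therefore fall well after planned titration. An unplanned step can fall later, because "if interruption occurs after Visit 4, subsequent up-titration will be allowed either at a scheduled visit or at an unscheduled visit". The documents do not say how often that would happen.

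**Which blood pressure values exist for an episode at home.**

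- The scheduled home reading is seated and before the morning dose.
- Protocol 1.2.1 puts peak concentration at 0.5–1.0 hour after dosing in healthy volunteers, and links peak concentration closely to orthostatic dysregulation.
- Post-dose vital signs at about 1 and 2 hours are taken only in clinic, at Visits 2 to 5 (Flow Chart footnote 23).

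A short post-dose episode at home therefore has a blood pressure value only if the patient decides to take an extra reading.

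**The case against.** The strongest objection is that the missing instruction may not be missing. A request to call the site would normally sit in patient-facing material. The patient information is not part of the public copy and the diary text is blacked out. This stands as a condition on the conclusion: those texts must be checked first. If they already require a call, 5.2.2.1 still needs to be brought into line with them.

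It can also be said that the sentence is about recording, not triage. It ensures that symptoms and readings reach the AE record, and it does not tell anyone to wait. Unscheduled visits exist, and a patient may stop dosing at will. All true, but an unscheduled visit needs a site that knows of the problem, and stopping tablets alone does not replace an investigator's decision on dose, restart or recall.

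A third argument is that the figures are only visit spacing, with no onset, frequency or harm data behind them. This is correct, and no mean delay is claimed. Several facts reduce the weight of the longer figures. The visit-day dose in titration is observed around its expected peak. The Visit 4 step is a true increase only in the high-dose arm. In Trial 1366-0020 orthostatic intolerance recovered on continued treatment, although that trial treated 49 patients for at most 4 weeks.

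Finally, the secondary endpoint rests on investigator judgement, so a report at the next visit still captures it, and stored readings are not lost. This also stands. The data argument touches only the lowest-pressure episode analysis, and no bias between arms is shown.

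**Conclusion.** The concern holds as a safety-wording improvement. It is not a statistical error or an internal contradiction. Taken literally, the instruction allows site awareness to lag by up to 7 to 28 days nominally, and 9 to 38 days with visit windows. The 7- to 14-day waits directly after the titration steps matter most; the 28-day waits are longer but start nominally six weeks after the last planned step.

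The conclusion assumes that visits stay within their windows (a missed visit would lengthen the wait), that the patient does no more than the sentence asks, and that the diary and patient information do not already ask for earlier contact. Confidence is medium because of that last assumption.

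**What to change.** In Protocol 5.2.2.1, state that a patient with symptoms suggestive of hypotension should take an extra BP and HR reading and contact the site the same day, so that the investigator can apply 4.1.4, 4.1.4.1, 4.1.4.2 and 6.1 promptly. Keep the report at the next visit as an additional record. Bring the diary and patient-information wording into line, and add nothing that implies other symptoms can wait. Where the instruction is followed, the delay in site awareness falls to about 0 days in every interval.

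The cost is one protocol sentence and the matching patient-facing text. The downside is some extra calls and possibly more mild AEs recorded. No dose, stopping rule or blood pressure threshold changes.
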